8.1.7 Independent Data Monitoring Committee

This study will be monitored by an external independent data monitoring committee (IDMC), which will conduct periodic reviews of safety data from all parts of the study (Section 12.3.6.2). Procedural details of the IDMC structure and function, frequency of meetings, and data planned for review will be included in the IDMC Charter. The IDMC Charter will be finalized before the first subject is screened.

8.2 Rationale for Study Design and Study Drug Regimens

8.2.1 Study Design

This Phase 2 study is the first study to assess combination therapy of VX-440 with TEZ and/or IVA in subjects with CF.

Parts 1 and 2 are designed to evaluate the safety and efficacy of the TC and to establish proof-of-concept in 2 populations of subjects defined by *CFTR* genotype: subjects heterozygous for the *F508del* mutation with a second *CFTR* allele carrying an minimal *CFTR* function mutation that is not expected to respond to TEZ/IVA (*F508del/MF*) (Part 1), and subjects homozygous for *F508del* (*F508del/F508del*) (Part 2) (See Section 8.2.3).

Based on in vitro data, TC is predicted to provide clinically relevant improvements in chloride transport in both populations greater than the individual compounds or any dual combinations. In Parts 1 and 2, efficacy will be evaluated through the assessment of spirometry and patient reported outcomes, and PD will be evaluated through the assessment of sweat chloride. Part 1 of the study will also obtain information regarding the exposure-response relationship (Section 12.1.2.1).

A Phase 3 study of TEZ/IVA in subjects with *F508del*/MF genotypes (Study VX14-661-107) was terminated following a planned interim futility analysis that showed that the combination of TEZ/IVA did not result in a prespecified improvement in lung function. Efficacy has not been established for a corrector, potentiator, or any corrector/potentiator combination in subjects with *F508del*/MF genotypes. Therefore, placebo is the comparator in Part 1.

A potential for benefit was demonstrated for TEZ/IVA in subjects with the *F508del*/*F508del* genotype in Study VX11-661-101.¹¹ Therefore, TEZ/IVA is the comparator in Part 2. In addition, Part 2 will have a 4-week run-in period to establish a reliable on-treatment (TEZ/IVA) baseline for comparison to the Treatment Period, when subjects will additionally receive VX-440 or placebo.

To measure off-treatment effects, Part 1 will include a Day 43 Visit, and Part 2 will include a VX-440 (or placebo) washout period.

[REDACTED]

Based on the mechanism of action of VX-440 and demonstration that VX-440 monotherapy provides little improvement in chloride transport in vitro, it is not expected that VX-440 monotherapy will be efficacious in vivo.

[REDACTED]

8.2.2 Study Drug Dose and Duration

VX-440 Dose

Part 1 will evaluate 2 dose levels of VX-440 in TC with TEZ/IVA in subjects with the *F508del*/MF genotype. The planned high dose of VX-440 to be evaluated as part of the TC (TC-1B-high) is 600 mg q12h which was the highest dose shown to be safe and well tolerated in TC in healthy subjects in Study 002. This dose was selected to ensure maximal clinical benefit based on the in vitro potency of VX-440 as part of the TC, while maintaining a margin of exposure relative to safety findings from nonclinical studies. The low dose (TC-1B-low) of 200 mg q12h is also predicted to provide clinical benefit based on in vitro data and was selected to provide a lower range of exposure for exposure-response analyses of safety and efficacy.

It is anticipated that differences in VX-440 PK may be observed in subjects with CF relative to healthy subjects, based on previous clinical experience with another CFTR corrector of similar dose range, LUM, where lower exposures were observed in subjects with CF relative to healthy subjects. Thus, the planned high dose of VX-440 (600 mg q12h) may result in lower exposure in

patients relative to the highest exposure evaluated in healthy subjects, if an effect similar to LUM is observed for VX-440. If VX-440 exposures in Cohort 1A are higher than that in healthy subjects at a comparable dose, then the high dose of VX-440 will be reduced from 600 mg q12h to 400 mg q12h.

Dose- and exposure-response information obtained from Part 1 (subjects with the *F508del*/MF genotype) is expected to be applicable to other populations with an *F508del* mutation, including subjects with the *F508del*/*F508del* genotype, based on similar in vitro potency for the TC in HBE cells with 1 or 2 copies of *F508del*.⁸

TEZ Dose

In Cohort 1A, TEZ will be administered as 100 mg qd, which is the same dose currently under evaluation in Phase 3 studies of TEZ/IVA. This dose of TEZ is appropriate for evaluation in the TC based on in vitro experiments with VX-440 which evaluated similar levels of TEZ exposure after correction for protein-binding. In Cohort 1B and Part 2, the dose of TEZ, when administered in the TC, will be 50 mg q12h so that all components of the TC are administered q12h; the total daily dose of TEZ (100 mg) will be the same as that under evaluation in Phase 3 studies of TEZ/IVA.

IVA Dose

In vitro data indicate that maintaining adequate IVA exposure in vivo will be important for maximizing efficacy of the TC. When administered in combination with VX-440 200 mg, the dose of IVA will be the same as the recommended dose for IVA monotherapy for patients aged 12 years and older (150 mg q12h). Preliminary data from Study 002 indicate that VX-440 is a moderate to strong inducer of CYP3A4. Because IVA is a sensitive CYP3A substrate, the dose of IVA will be increased from 150 mg q12h to 300 mg q12h when it is administered with VX-440 at a dose level of 600 mg q12h. These dose levels were evaluated in Study 002 and were safe and well tolerated. At these dose levels, IVA exposure was approximately 50% lower relative to IVA 150 mg q12h monotherapy based on historical data.¹² If the high dose of VX-440 is reduced to 400 mg q12h, the IVA dose will remain 300 mg q12h, as VX-440 induction is predicted to be similar in magnitude at this dose relative to 600 mg q12h. Phase 3 and post-approval data for IVA monotherapy have not revealed any systemic exposure-related safety findings and indicate a wide therapeutic margin for safety. Use of a higher IVA dose when coadministering IVA with a CYP3A inducer is consistent with the approach for combination therapy with LUM (a strong CYP3A inducer). In that combination therapy, the IVA dose is 250 mg q12h.

Treatment Duration

The 4-week treatment duration in Parts 1 and 2 is based on previous experience with CF correctors and potentiators in clinical studies of subjects with CF. Based on preliminary data from Studies 001 and 002, and data from previous studies of TEZ and IVA, all components of the TC reach steady-state levels of exposure by 2 to 3 weeks. In previous studies of TEZ and IVA, PD effects were observed within 4 weeks of treatment. In Study VX06-770-101, treatment with IVA for 28 days resulted in statistically significant within-group changes from baseline in ppFEV₁ as well as a trend toward clinically meaningful improvements in the respiratory domain of the CFQ-R; differences in biomarkers of CFTR activity (sweat chloride) between IVA and placebo groups were also demonstrated. Furthermore, in Study VX11-661-101 dose-dependent

improvements in lung function were observed for TEZ/IVA after 4 weeks of treatment, with the 2 highest dose groups showing statistically significant improvement in lung function versus placebo.¹¹ In both studies, improvements in sweat chloride and ppFEV₁ were observed as rapidly as 3 to 7 days after the start of dosing, with most of the effect observed within 14 days. Given the increased in vitro response of the TC relative to TEZ/IVA, it is expected that the 4-week treatment duration in Parts 1 and 2 will be sufficient to observe differences between treatment arms with respect to efficacy and PD endpoints.

[REDACTED]

8.2.3 Rationale for Study Population

The study will include subjects with *F508del*/MF and *F508del*/*F508del* genotypes based on in vitro data that indicate the potential for significant improvements in chloride transport for CF patients with 1 or 2 copies of the *F508del* mutation in response to treatment with TC compared to individual compounds and all dual combinations. The subjects will be evaluated by genotype in separate cohorts in Parts 1 and 2, based on the potential for differences in the magnitude of treatment response among the 2 genotype categories.

Adult subjects (age 18 years or older) will be enrolled in Parts 1 and 2. Pending demonstration of acceptable safety and the potential for benefit based on efficacy results in Part 1, [REDACTED]

[REDACTED]

8.2.4 Rationale for Study Assessments

[REDACTED]

The PD and efficacy assessments are widely accepted and generally recognized as reliable, accurate, and relevant to the study of patients in CF. All assessments, [REDACTED] [REDACTED] were routinely measured in the registration studies of IVA (Kalydeco) or LUM/IVA combination therapy (Orkambi). [REDACTED]

[REDACTED]

9 STUDY POPULATION

Eligibility will be reviewed and documented by an appropriately qualified member of the investigator's team before subjects are randomized (Parts 1 [REDACTED] or receive TEZ/IVA in the Run-in Period (Part 2).

9.1 Inclusion Criteria

1. Subject (or subject's legally appointed and authorized representative) will sign and date an informed consent form (ICF), and, when appropriate, an assent form.
2. Willing and able to comply with scheduled visits, treatment plan, study restrictions, laboratory tests, contraceptive guidelines, and other study procedures.

4. Body weight ≥ 35 kg.
5. Sweat chloride value ≥ 60 mmol/L from test results obtained during screening. If the value cannot be determined from the screening test, a sweat chloride value documented in the subject's medical record may be used to establish eligibility. (It is acceptable to use a sweat chloride value that was obtained before previous treatment with IVA, LUM/IVA, or an investigational CFTR modulator).
6. Subjects must have an eligible *CFTR* genotype as noted below. If the screening *CFTR* genotype result is not received before randomization (Parts 1 [REDACTED] or before Day -28 (Part 2), a previous *CFTR* genotype laboratory report may be used to establish eligibility. Note: Subjects who have been randomized and whose screening genotype does not confirm study eligibility must be discontinued from the study (Section 9.5).
 - Part 1 [REDACTED]: Heterozygous for *F508del* with a second *CFTR* allele carrying an MF mutation that is not likely to respond to TEZ and/or IVA therapy (Appendix A)
 - Part 2: Homozygous for *F508del*
7. Parts 1, 2, [REDACTED] subjects must have an $FEV_1 \geq 40\%$ and $\leq 90\%$ of predicted normal for age, sex, and height (equations of the Global Lung Function Initiative [GLI])¹³ at the Screening Visit. Spirometry measurements must meet American Thoracic Society/European Respiratory Society criteria¹⁰ for acceptability and repeatability.
8. Stable CF disease as judged by the investigator.
9. Willing to remain on a stable CF medication regimen through the planned end of treatment or, if applicable, the Safety Follow-up Visit.

9.2 Exclusion Criteria

1. History of any comorbidity that, in the opinion of the investigator, might confound the results of the study or pose an additional risk in administering study drug to the subject.
2. History of cirrhosis with portal hypertension.
3. Risk factors for Torsade de Pointes, including but not limited to, history of any of the following: familial long QT syndrome, chronic hypokalemia, heart failure, left ventricular hypertrophy, chronic bradycardia, myocardial infarction, cardiomyopathy, history of arrhythmia (ventricular or atrial fibrillation), obesity, acute neurologic events (subarachnoid hemorrhage, intracranial hemorrhage, cerebrovascular accident, or intracranial trauma), or autonomic neuropathy.
4. History of hemolysis.
5. G6PD deficiency, defined as G6PD activity less than the lower limit of normal (LLN) or 70% of the mean of the LLN and the ULN, whichever is greater.
6. Any of the following abnormal laboratory values at screening:
 - Hemoglobin <10 g/dL
 - Total bilirubin $\geq 2 \times$ ULN
 - Aspartate aminotransferase (AST), alanine aminotransferase (ALT), gamma-glutamyl transpeptidase (GGT), or alkaline phosphatase (ALP) $\geq 3 \times$ ULN
 - Abnormal renal function defined as glomerular filtration rate ≤ 50 mL/min/1.73 m² (calculated by the Modification of Diet in Renal Disease Study Equation)^{14, 15} for subjects ≥ 18 years of age and ≤ 45 mL/min/1.73 m² (calculated by the Counahan-Barratt equation)¹⁶ for subjects aged 12 to 17 years (inclusive)
7. An acute upper or lower respiratory infection, pulmonary exacerbation, or changes in therapy (including antibiotics) for pulmonary disease within 28 days before the first dose of study drug (Day 1 for Parts 1 [REDACTED] Day -28 for Part 2).
8. Lung infection with organisms associated with a more rapid decline in pulmonary status (e.g., *Burkholderia cenocepacia*, *Burkholderia dolosa*, and *Mycobacterium abscessus*). For subjects who have had a history of a positive culture in the past, the investigator will apply the following criteria to establish whether the subject is free of infection with such organisms:
 - The subject has had 2 respiratory tract cultures negative for these organisms within the past 12 months, with no subsequent positive cultures.
 - These 2 respiratory tract cultures were separated by at least 3 months, and 1 of them was obtained within the past 6 months.
9. An acute illness not related to CF (e.g., gastroenteritis) within 14 days before the first dose of study drug (Day 1 for Parts 1 [REDACTED] Day -28 for Part 2).

10. A standard digital ECG demonstrating QTc >450 msec at screening. If QTc exceeds 450 msec for the screening ECG, the ECG should be repeated 2 more times during the Screening Period, and the subject will be excluded if the average of the 3 QTc values is >450 msec.
11. History of solid organ or hematological transplantation.
12. History or evidence of cataract or lens opacity determined to be clinically significant by the ophthalmologist or optometrist based on the ophthalmologic examination during the Screening Period. If there is documentation of an examination meeting protocol criteria that was conducted within 3 months before the date of informed consent (or assent, when applicable), then the ophthalmologic examination does not need to be repeated during the Screening Period. This criterion does not apply to subjects with documentation of bilateral lens removal, and the ophthalmologic examination is not required for these subjects at screening.
13. History of alcohol or drug abuse in the past year, including but not limited to, cannabis, cocaine, and opiates, as deemed by the investigator.
14. Ongoing or prior participation in an investigational drug study with the exception of the following:
 - Ongoing or prior participation in an investigational study of TEZ/IVA, IVA, LUM/IVA, or other CFTR modulator. For Parts 1 [REDACTED] a washout period of 28 days must elapse before Day 1. Subjects participating in Study 661-110 may have the Part 1 [REDACTED] Screening Period extended by 4 weeks (Section 8.1.1.3). For Part 2, a washout period before Day -28 is not required, and subjects participating in Study 661-110 will transition directly from their prior treatment to the TEZ/IVA Run-in Period providing that they meet eligibility criteria. For all parts, subjects participating in Study 661-110 may have their screening assessments performed while continuing to participate in Study 661-110.
 - For prospective subjects with ongoing or prior participation in all other interventional studies, a washout period of 28 days or 5 terminal half-lives, whichever is longer, must elapse before screening. The duration of the elapsed time may be longer if required by local regulations.
 - Ongoing participation in a noninterventional study (including observational studies and studies requiring assessments without administration of study drug or assignment to other interventions) is permitted.
15. Use of commercially available CFTR modulator (e.g., Kalydeco, Orkambi) within 14 days before screening (Parts 1 [REDACTED]).
16. Use of restricted medications as defined in Table 9-1, within the specified window before the first dose of study drug (Day 1 in Parts 1 [REDACTED], Day -28 in Part 2).
17. Pregnant or nursing females: Females of childbearing potential must have a negative pregnancy test at screening and Day 1.
18. The subject or a close relative of the subject is the investigator or a subinvestigator, research assistant, pharmacist, study coordinator, or other staff directly involved with the conduct of

the study. An adult (aged 18 years or older) who is a relative of a study staff member may be randomized in the study provided that

- the adult lives independently of and does not reside with the study staff member, and
- the adult participates in the study at a site other than the site at which the family member is employed.

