10.4 Study Drug Interruption and Stopping Rules

Subjects with new treatment-emergent ALT or AST elevations of $>3 \times \text{ULN}$, or total bilirubin $>2 \times \text{ULN}$, must be followed closely, including confirmatory testing performed by the central laboratory within 48 to 72 hours of the initial finding and subsequent close monitoring of ALT, AST, and bilirubin levels, as clinically indicated.

If a subject cannot return to the site for confirmatory testing, a local laboratory may be used. Local laboratory results must be reported immediately to the medical monitor, and the subject must have the tests repeated and sent to the central laboratory as soon as possible (ideally within 48 to 72 hours).

Study drug administration **must be interrupted** immediately (prior to confirmatory testing), and the medical monitor must be notified, if any of the following criteria are met:

- ALT or AST $>8 \times \text{ULN}$
- ALT or AST $>5 \times \text{ULN}$ for more than 2 weeks

- ALT or AST $>3 \times$ ULN, in association with total bilirubin $>2 \times$ ULN and/or clinical jaundice
- Indirect bilirubin $>2 \times$ ULN (defined as ULN for total bilirubin minus ULN for direct bilirubin)

A thorough investigation of potential causes should be conducted, and the subject should be followed closely for clinical progression.

Study drug administration **must be discontinued**, if either of the following criteria is met:

- Subsequent ALT or AST values confirm the initial elevation that satisfied the interruption rule (above), and no convincing alternative etiology (e.g., acetaminophen use, viral hepatitis, or alcohol ingestion) is identified, regardless of whether transaminase levels have improved
- Indirect bilirubin $>2 \times$ ULN (defined as ULN for total bilirubin minus ULN for direct bilirubin), in association with decreased haptoglobin

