If an alternative, reversible cause of transaminase elevation and/or increased bilirubin or clinical jaundice has been identified, study drug administration may be resumed once transaminases or bilirubin return to baseline or are $\leq 2 \times$ ULN, whichever is higher. Approval of the medical monitor is required before resumption of study drug. Upon resumption of study drug, transaminases and bilirubin should be assessed weekly for 4 weeks. If a protocol-defined transaminase or bilirubin elevation interruption threshold recurs within 4 weeks of rechallenge with the study drug (with confirmation of the initial elevation by repeat testing within 48 to 72 hours), then the study drug must be permanently discontinued, regardless of the presumed etiology.

All subjects in whom treatment is discontinued for elevated transaminases and/or bilirubin should have these levels monitored closely until levels normalize or return to baseline.

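### Exclusion 6 limits only total bilirubin, so a subject can be eligible while already meeting the indirect-bilirubin interruption criterion in Protocol 10.4, and the rules that follow do not handle a stable baseline value coherently

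*Protocol*

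**What the plan says.** **Entry.** Protocol 9.2, criterion 6 applies to screening values ("Any of the following abnormal laboratory values at screening"). Its only bilirubin limit is "Total bilirubin $\geq 2 \times$ ULN". SAP Appendix D repeats it unchanged as an important-protocol-deviation rule. No eligibility criterion mentions indirect bilirubin.

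**Interruption.** Protocol 10.4 requires study drug to be interrupted at once, before confirmatory testing, "and the medical monitor must be notified, if any of the following criteria are met". One criterion is indirect bilirubin above 2 x ULN, with that ULN "defined as ULN for total bilirubin minus ULN for direct bilirubin".

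**Discontinuation.** On indirect bilirubin, 10.4 requires discontinuation only when the same elevation occurs "in association with decreased haptoglobin".

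**Resumption and recurrence.** Drug may resume, with medical monitor approval, once values are back to baseline or at most 2 x ULN, whichever is higher. The opening condition is "If an alternative, reversible cause of transaminase elevation and/or increased bilirubin or clinical jaundice has been identified". If an interruption threshold is met again within 4 weeks of rechallenge and is confirmed, discontinuation is permanent whatever the presumed cause.

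**The concern.** The entry rule and the interruption rule use different quantities with different reference limits. Because the indirect ULN is the total ULN minus the direct ULN, it is smaller than the total ULN. Twice the smaller limit can therefore be exceeded while total bilirubin is still under twice the larger one.

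The other interruption criteria do not overlap with eligibility. ALT and AST must be below 3 x ULN to enter. The transaminase triggers are above 8 x ULN, above 5 x ULN for more than 2 weeks, and above 3 x ULN together with raised total bilirubin or jaundice. Only the indirect-bilirubin criterion can already be met by an eligible subject.

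At stake is treatment exposure. A subject whose value has not changed since screening could be interrupted on a protocol rule, with no clear way to restart, in a part of the trial where treatment lasts 4 weeks.

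**Working it through.** The plan states no figure on this point, so there is none to reproduce. The check is whether both rules can hold at once.

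**Notation.** T = ULN for total bilirubin, D = ULN for direct bilirubin, I = the subject's indirect bilirubin, d = the subject's direct bilirubin. Total bilirubin is I + d.

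**Step 1: the two rules**

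- Eligible (9.2, criterion 6): I + d < 2T, so I < 2T - d.
- Interrupt (10.4): I > 2(T - D).

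**Step 2: the overlap**

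- Both hold for 2(T - D) < I < 2T - d.
- The interval is non-empty exactly when 2T - 2D < 2T - d, that is, when d < 2D.
- As a multiple of the total ULN, the overlap in total bilirubin starts at [2(T - D) + d]/T = 2 - (2D - d)/T and ends at 2.

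This needs only D > 0 and no outside figure.

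**Step 3: size under assumed reference ranges.** The documents give no ULNs. The values below are assumptions in mg/dL, with d set at half of D and at D.

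| T | D | d | Trigger 2(T-D) | Eligible total below 2T | Overlap in total starts at 2(T-D)+d | Start as multiple of T |
|---|---|---|---|---|---|---|
| 1.0 | 0.2 | 0.1 | 1.6 | 2.0 | 1.70 | 1.70 |
| 1.0 | 0.2 | 0.2 | 1.6 | 2.0 | 1.80 | 1.80 |
| 1.2 | 0.3 | 0.15 | 1.8 | 2.4 | 1.95 | 1.625 |
| 1.2 | 0.3 | 0.3 | 1.8 | 2.4 | 2.10 | 1.75 |
| 1.2 | 0.2 | 0.1 | 2.0 | 2.4 | 2.10 | 1.75 |
| 1.2 | 0.2 | 0.2 | 2.0 | 2.4 | 2.20 | 1.83 |
| 1.1 | 0.4 | 0.2 | 1.4 | 2.2 | 1.60 | 1.45 |
| 1.1 | 0.4 | 0.4 | 1.4 | 2.2 | 1.80 | 1.64 |

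The lower end runs from 1.45 to 1.83. On a wider grid (T from 1.0 to 1.3, D from 0.2 to 0.4) it is 1.60 to 1.85 with d = D, and 1.30 to 1.77 with d = 0.1. The overlap vanishes once d reaches 2D.

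**Step 4: one subject.** Take T = 1.2, D = 0.3, total 2.2 and direct 0.3. Total is 2.2/1.2 = 1.83 x ULN, so the subject is eligible. Indirect is 2.2 - 0.3 = 1.9 against an indirect ULN of 0.9, and 1.9/0.9 = 2.11, so the interruption criterion is met.

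**Step 5: follow a stable value through 10.4**

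1. The criterion is met and drug is interrupted.
2. Without decreased haptoglobin, discontinuation on indirect bilirubin does not apply.
3. The numerical condition for resumption is met at once: the value is at baseline, and total bilirubin is below 2 x ULN. But resumption also needs a reversible alternative cause, and a stable trait may have none. The subject is then neither discontinued nor able to restart.
4. If a cause is accepted and drug restarts, bilirubin is tested weekly for 4 weeks. The unchanged value meets the threshold again, and confirmation forces permanent discontinuation.

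**Step 6: arm sizes.** From the planned numbers and ratios: TC-1A is 10 x 4/5 = 8. TC-1B-high and TC-1B-low are 32 x 2/4 = 16 and 32 x 1/4 = 8. TC-2 is 24 x 3/4 = 18. One subject is 1/8 = 12.5% of TC-1A or TC-1B-low, and 1/16 = 6.25% of TC-1B-high or of the pooled TC-1A and TC-1B-low group used in the primary model (SAP 8.3.1.1). These are the weight of one subject, not an expected frequency.

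**The case against.** **Scope.** Section 10.4 opens with "Subjects with new treatment-emergent ALT or AST elevations of" more than 3 x ULN, or total bilirubin more than 2 x ULN, and sets confirmatory testing for those subjects. The interruption sentence refers to confirmatory testing, so the whole section could be read as confined to new elevations. The reading is reasonable but does not settle the matter. The opening sentence concerns ALT, AST and total bilirubin, and a subject in the overlap has total bilirubin below 2 x ULN and need not have raised transaminases. The interruption list has its own lead-in without that limit. If new elevations were intended, the text needs to say so.

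**Baseline is already considered.** It is, but only in the resumption level. It would go too far to say that 10.4 ignores raised baselines or that drug can never restart. What remains is that the triggers, the reversible-cause condition and the recurrence rule do not take baseline into account.

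**A false haemolysis signal.** A reader might infer that these interruptions would put a spurious haemolysis signal into the safety results. The documents do not support that. Protocol 13.1.1.2 makes a laboratory finding an AE only on clinically significant worsening from baseline, and SAP 8.4.1 counts only new or worsened events. SAP Appendix I has thresholds for total and direct bilirubin but none for indirect.

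**Part 2.** A reader might infer that TC-2 subjects would be randomised and then interrupted. TEZ/IVA is itself study drug and chemistry is drawn on Day -28, so a stable raised value would normally appear in the Run-in, before randomisation.

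**Few subjects, and a cautious direction.** Both stand. The band is narrow, and criteria 1, 4 and 5 may remove some of these subjects, although none limits indirect bilirubin. The mismatch leads to withholding drug with the medical monitor informed, so it should not be described as rules that contradict each other on patient safety. SAP 8.3 keeps measurements after treatment discontinuation in the efficacy analysis, so the loss is of exposure rather than of data.

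**Conclusion.** The inconsistency is real and the text is wrong as written. Criterion 6 admits subjects who already meet the indirect-bilirubin interruption criterion, for any positive direct ULN and any direct bilirubin below twice that ULN. That part rests on the documents alone. The illustrative size, total bilirubin from about 1.45-1.83 up to 2.0 x ULN, depends on the assumed reference ranges. The number of affected subjects cannot be estimated from the documents.

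The consequence is limited to possible avoidable interruption and lost exposure, in active arms of about 8 to 18 with 4 weeks of VX-440 or placebo. In Part 2 it would normally arise on TEZ/IVA in the Run-in. Interruption is the mandatory step, and discontinuation on indirect bilirubin needs decreased haptoglobin as well. Nothing here shows bias in the efficacy comparison or a distorted safety table.

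**What to change.** Reconcile Protocol 9.2 (criterion 6), Protocol 10.4 and SAP Appendix D so that the entry, interruption, resumption and recurrence rules are mutually consistent for an indirect bilirubin value already present at baseline. The text should say whether the interruption list applies to such a value, and how the resumption and recurrence provisions then operate. Which rule or threshold prevails is for the sponsor; none is proposed here.

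The cost is a wording change in the protocol, with SAP Appendix D updated if criterion 6 changes. No new sample is needed, because total and direct bilirubin are both in the serum chemistry panel (Protocol Table 11-2), which is drawn at screening.
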